## DOCUMENT HISTORY

Document	Date of Issue	Approver(s)	Summary of Change
Original Protocol	18-May-2018		Not applicable
Amendment 01	15-Jun-2018		Clarified that Psoriasis Symptoms and Signs Diary (PSSD) daily data collection will begin at the Screening Visit and, for randomized subjects, will continue daily through Week 52.
Amendment 02	17-Jul-2018		Japan-Specific Amendment
Amendment 03	03-Oct-2018		China-Specific Amendment

Amendment 04	20-Nov-2018		Updated the Sponsor's contact information, made typographic corrections to the protocol, clarified certain procedures, updated wording in Appendix 3 to be consistent across studies of BMS-986165, described treatment assignment details, and revised certain exclusion criteria to be consistent with certain elements of the Phase 2 study of BMS-986165 in psoriasis as well as other Phase 3 studies in psoriasis
Amendment 05	12-Dec-2018		German-Specific Amendment
Amendment 06	14-May-2019		As this is designed to be a global study across multiple countries, randomization in each country will be targeted to approximately 35% or less of the total sample size. This change is being implemented to achieve geographical representation across countries and to minimize the potential for any single country to have a disproportionate impact on the overall efficacy and/or safety profile. Other changes include:

			
-Updated text in the definition of sPGA in Section 8.1.1.1 to be consistent with the description in Appendix 5.
 
[REDACTED]

Amendment 07	06-June-2019	[REDACTED]	
Revised the testing order (hierarchy) of key secondary endpoints [REDACTED] revised the text in the synopsis, Table 4 and in Sections 9.3.2.1 and 9.3.2.2 accordingly as follows:
 

• Removed endpoints containing 'PSSD sign score.' The reason for this change is that PSSD sign score is redundant with components assessed by PASI and sPGA which are already in the hierarchy.

• Removed 'change from baseline in DLQI score.' The reason for this change is that DLQI endpoint 'DLQI 0/1 among subjects with baseline DLQI score <math>\geq 2</math>' is clinically meaningful and is already in the hierarchy.

• Changed the comparisons to apremilast from 'sPGA 0/1 at Week 52', 'PASI 75 at Week 52', and 'PASI 90 at Week 52' to 'sPGA 0/1 at Week 52 and Week 24', 'PASI 75 at Week 52 and Week 24', and 'PASI 90 at Week 52 and Week 24'. The reason for these changes is to assess maintenance of effect.

Amendment 08	24-Jun-2019		China-Specific Amendment
Amendment 09	12-Jul-2019		Germany-Specific Amendment – Included changes listed above for Global Amendments 04, 06 and 07
Global Revised Protocol 10	17-Dec-2019		
Made the following updates:
 

• provided clarifications in the protocol to aid sites and subjects in the conduct of the study.

• added and updated relevant protocol deviation criteria for the Per Protocol Set

• corrected typographical errors

• added a new analysis for systemic treatment- naïve subjects to the set of subgroup analysis for the coprimary efficacy endpoints

## SUMMARY OF CHANGES

### Rationale:

The primary purpose of this global revised protocol is to provide clarifications in the protocol to aid sites and subjects in the conduct of the study.

Key modifications and clarifications are summarized as follows:

- Add clarifying detail to several items in the protocol
- [REDACTED]
- Added and updated relevant protocol deviation criteria for the Per Protocol Set
- Added a new analysis for systemic treatment-naïve subjects to the set of subgroup analysis for the coprimary efficacy endpoints

[figure not shown]
Substantive changes made to the previous version of the global protocol and the rationale for these changes are noted below in the summary of key changes table. All changes applied to the protocol body were applied to the synopsis, as necessary; synopsis changes are not included in the summary of key changes table. Only major additions and deletions are provided in this summary document; all minor grammatical, formatting, stylistic changes, or clarifications as well as organizational changes are not included.

Protocol Section	Revised Protocol Text	Rationale for Change
Schedule of Assessments Table 3	Removed Targeted PE from the Week 52 visit	There is already a scheduled Full PE for the Week 52 visit.

Protocol Section	Revised Protocol Text	Rationale for Change
4.1.6.2 Infection Adjudication Committee	Updated text to: An independent Infection Adjudication Committee, composed of individuals with relevant expertise, will blindly review and adjudicate infection AEs, such as opportunistic infections, influenza, herpes zoster, and TB, reported in the study per criteria specified in a separate charter .	
4.1.6.3 CV Committee	An independent Cardiovascular (CV) Adjudication Committee, composed of individuals with relevant expertise, will blindly review and adjudicate cardiovascular and cerebrovascular AEs such as, but not limited to, Major Adverse Cardiovascular Events (MACE) that include death, non-fatal myocardial infarction, non-fatal stroke; revascularization procedures; heart failure; dysrhythmias; heart blocks; and thrombotic events reported in the study per criteria specified in a separate charter .	To clarify that the data will be reviewed in a blinded manner by the study's Adjudication committees.
4.1.6.4 Suicidal Ideation and Behavior Adjudication Committee	An independent Suicidal Ideation and Behavior Adjudication Committee, composed of individuals with relevant expertise, will blindly review and adjudicate suicidal ideation/behavior reported in the study per criteria specified in a separate charter .	
5.3 Lifestyle Restrictions	Updated text: General skin care measures (with above restrictions for topical treatments) that are standard for patients with plaque psoriasis are permitted .	To clarify general skin care measures used in the trial.

Protocol Section	Revised Protocol Text	Rationale for Change
6.7.1 Prohibited and/or Restricted Treatments	
Updated or added text:
 
7) Any use of oral psoriasis medications (eg, methotrexate, cyclosporine, retinoids, fumaric acid derivatives) for any indication
 
8) Any use of oral or injectable corticosteroids (prednisone, methylprednisolone, etc.), unless it is considered necessary for the subject's welfare and/or treatment of an AE/SAE
 
Note: otic, ophthalmic, nasal, or inhaled corticosteroids within recommended doses and with no systemic effects are permitted
 
9) Any topical medications/treatments, which are used for any indication, that could affect psoriasis evaluation (including, but not limited to, high potency corticosteroids (WHO Classes I-V), >3% salicylic acid, urea, alpha- or beta-hydroxyl acids, anthralin, calcipotriene, vitamin D derivatives, retinoids, tazarotene, methoxsalen, trimethylpsoralens, pimecrolimus, and tacrolimus)
 
Exception: The following topical treatments may be initiated only at Week 24 per investigator's discretion in subjects who have sPGA scores <math>\geq 3</math> (See Section 4.1.4):
 
 
High potency corticosteroids (WHO Classes I-V), >3% salicylic acid, urea, alpha- or beta hydroxyl acids, anthralin, calcipotriene, vitamin D derivatives, retinoids, tazarotene
 
 
Note: Low potency topical steroids (WHO Classes VI and VII) are permitted on the palms, soles, face, and intertriginous areas but should not be used within 24 hours prior to any study visit. Bland emollients (defined as emollients without urea or alpha or beta-hydroxy acids or other ingredients which are pharmaceutically active) are allowed on all body regions but should not be used within 24 hours prior to any study visit.
	Added clarifying detail around these prohibited medications
6.7.2 Permitted Concomitant Medications	
Note: Low potency topical steroids (WHO Classes VI and VII) are permitted on the palms, soles, face, and intertriginous areas but should not be used within 24 hours prior to any study visit. Bland emollients (defined as emollients without urea or alpha or beta hydroxyl acids or other ingredients which are pharmaceutically active) are allowed on all body regions but should not be used within 24 hours prior to any study visit.
	Added clarifying detail around these medications
8.4.7 Suicidal Ideation and Behavior Monitoring	
Subjects who answer yes to Questions 4 or 5 which indicates a suicidal ideation severity level of 4 or 5 or document suicidal behavior or suicidal attempts on the eC-SSRS will have their treatments discontinued and be immediately referred to a mental health professional for further evaluation.
	Clarified to sites to what levels of suicidal ideation Questions 4 and 5 refer.

Protocol Section	Revised Protocol Text	Rationale for Change

Protocol Section	Revised Protocol Text	Rationale for Change
9.2 Populations for Analyses	
Changed to:
 
Full Analysis Set (FAS): All subjects who were randomized to receive assigned study treatment. Following the intent-to-treat principle, subjects will be analyzed according to the treatment group assigned at randomization. The FAS will be the primary efficacy analysis population.
 
Per Protocol Set (PPS): A subset of the FAS who are compliant with study treatment and who do not have any relevant protocol deviations that may impact the coprimary efficacy endpoint assessments (Section 9.6.3). The PPS will be analyzed for the coprimary endpoint comparison according to the treatment assigned at randomization.
 
As-treated Population: All randomized subjects who take at least one dose of study treatment. Subjects will be analyzed according to treatment received. The As-treated population will be for safety analyses.
 	To align populations for testing coprimary efficacy endpoints in order and to clarify that Per Protocol set will be a subset of FAS to assess the sensitivity of coprimary endpoints results based on FAS with respect to data irregularity and deviations
9.4.1.4 Subgroup Analyses for the Coprimary Endpoints	Added: Prior systemic treatment of psoriasis (yes/no)	To determine whether treatment effect sizes of BMS-986165 compared to placebo are similar or how much different with respect to prior use of systemic treatment affects

Protocol Section	Revised Protocol Text	Rationale for Change
9.6.3 Relevant Protocol Deviations	
Changed to:
 
Relevant protocol deviations are deviations that can have an impact on the primary efficacy endpoints. The impact of relevant protocol deviations on the primary efficacy results will be assessed by excluding subjects from the FAS to define the PPS in supportive analyses of the primary efficacy endpoints.
 
Relevant protocol deviations to be considered regarding exclusion of subjects from the FAS will include the following:
 
Subject randomized but did not take any study treatment
 
Subject failed to meet study inclusion criteria but was randomized to receive study treatment
 
Subject met a study exclusion criterion which may have an impact on the coprimary efficacy endpoints but was randomized to receive study treatment
 
Subject non-compliant with study treatment within the first 16 weeks of treatment; defined as <80% compliant with study treatment
 
Subject took prohibited concomitant medication prior to Week 16
 
Subject received treatment different to intended treatment at any visit prior to Week 16
 
All subjects with relevant protocol deviations will be identified prior to database lock. Relevant protocol deviations will be summarized by treatment group and deviation category for the FAS population.
	To clarify and document the final list of relevant protocol deviations for Per Protocol Analysis.

[figure not shown]

## 1 PROTOCOL SUMMARY

### 1.1 Synopsis

**Protocol Title:** A Multi-Center, Randomized, Double-Blind, Placebo- and Active Comparator-Controlled Phase 3 Study to Evaluate the Efficacy and Safety of BMS-986165 in Subjects with Moderate-to-Severe Plaque Psoriasis

**Short Title:** Efficacy and Safety of BMS-986165 versus Placebo and Active Comparator in Subjects with Psoriasis

**Study Phase:** 3

#### **Rationale:**

BMS-986165 is being evaluated as a therapeutic option for the treatment of subjects with moderate-to-severe plaque psoriasis based on results of a recently completed 12-week, randomized, Phase 2, placebo-controlled, parallel-group study (Study IM011011). The Phase 2 study was conducted with the following 5 different BMS-986165 treatment arms: 3 mg every other day (QOD); 3 mg once daily (QD); 3 mg twice daily (BID); 6 mg BID; and 12 mg QD. Overall, 267 subjects were randomized (44 to 45 subjects per treatment arm) in the Phase 2 study. All BMS-986165 treatment groups, except 3 mg QOD, achieved the primary endpoint of superiority compared with placebo in the proportion of subjects experiencing at least a 75% improvement in the Psoriasis Area and Severity Index (PASI 75) after 12 weeks of treatment. Compared with the placebo treatment group (6.7%), 38.6% ( $p = 0.0003$ ), 68.9% ( $p < 0.0001$ ), 66.7% ( $p < 0.0001$ ) and 75% ( $p < 0.0001$ ) of the subjects treated with BMS-986165 at 3 mg QD, 3 mg BID, 6 mg BID and 12 mg QD doses achieved a PASI 75 response, respectively. The PASI 75 responses appear to plateau at the dose of 3 mg BID. The current Phase 3 study is designed to confirm the efficacy and safety of BMS-986165 6 mg QD which is expected to have equivalent efficacy as the 3 mg BID dose in Phase 2, in a larger global population of subjects with stable moderate-to-severe plaque psoriasis.

#### **Study Population:**

Men and women  $\geq 18$  years of age diagnosed with stable (defined as no morphology changes or significant flares of disease activity in the opinion of the investigator) plaque psoriasis for  $\geq 6$  months and with moderate-to-severe disease by involvement of  $\geq 10\%$  of body surface area (BSA), static Physician's Global Assessment (sPGA)  $\geq 3$ , PASI score  $\geq 12$ , and candidates for phototherapy or systemic therapy will be eligible to participate in the study.

**Objectives and Endpoints:**

Objective	Endpoint
Primary	

Assess whether BMS-986165 is superior to placebo at Week 16 in the treatment of subjects with moderate-to-severe plaque psoriasis

	

sPGA 0/1

PASI 75

Selected Secondary Endpoints	

Assess whether BMS-986165 is superior to apremilast at Week 16

	

sPGA 0/1

PASI 75

PASI 90

sPGA 0

PASI 100

Assess whether BMS-986165 is superior to apremilast at Week 52

	

sPGA 0/1

PASI 75

PASI 90

sPGA 0

PASI 100

Assess whether BMS-986165 is superior to placebo over the first 16 weeks of treatment

	

sPGA 0/1

PASI 75

PASI 90

sPGA 0

PASI 100

Assess whether BMS-986165 is superior to apremilast over 52 weeks of treatment

	

sPGA 0/1

PASI 75

PASI 90

sPGA 0

PASI 100

Evaluate improvement in patient-reported outcomes for BMS-986165 compared with placebo through Week 16

Evaluate improvement in patient-reported outcomes for BMS-986165 compared with apremilast through Week 24

	

Change from baseline in Psoriasis Symptoms and Signs Diary (PSSD) symptom score, sign score, and total score

Change from baseline in Dermatology Life Quality Index (DLQI) score

Objective	Endpoint

### Overall Design:

This will be a 52-week, multi-center, randomized, double-blind, double-dummy, placebo- and active comparator-controlled study in subjects with stable moderate-to-severe plaque psoriasis. Subjects will undergo screening evaluations within 28 days prior to administration of study medication to determine eligibility. Following the screening process, approximately 600 qualified subjects will be randomized in a 2:1:1 ratio to one of the following 3 treatment groups:

- BMS-986165 6 mg QD
- Placebo
- Apremilast 30 mg BID (with initial titration per label) as active comparator

Randomization should not occur until at least 8 days after the Screening Visit to allow collection of PSSD data during screening in order to calculate a baseline PSSD score. Randomization will be stratified by geographic region (U.S., Japan [body weight stratum will not be applied in Japan], China [body weight stratum will not be applied in China], and Rest of World), previous biologic use (for psoriasis, psoriatic arthritis or other inflammatory diseases only; yes/no), and body weight ( $\geq 90$  kg and  $< 90$  kg). If subjects from China are not enrolled in the study, then the stratification level for China will not be utilized. As this is designed to be a global study across multiple countries, randomization in each country will be targeted to approximately 35% or less of the total sample size. This change is being implemented to achieve geographical representation across countries and to minimize the potential for any single country to have a disproportionate impact on the overall efficacy and/or safety profile.

At Week 16, subjects receiving placebo will be switched in a blinded manner to BMS-986165 6 mg QD. Subjects who are randomized to BMS-986165 6 mg QD or apremilast 30 mg BID will continue their current dose through Week 52.

At Week 24, subjects originally randomized to apremilast 30 mg BID who do not achieve PASI 50 response will be switched in a blinded manner to BMS-986165 6 mg QD; those who achieve PASI 50 response will continue to receive their current regimen through Week 52. A subject with sPGA  $\geq 3$  at Week 24 may be treated with restricted topical medications, such as topical high

potency corticosteroids (WHO Classes I-V), only at this time point at the discretion of the investigator.

Subjects who discontinue study treatment early should remain in the study for protocol-specified procedures (Please refer to Section 7.1 for more details). Those completing 52 weeks of treatment will be offered the opportunity to roll over to a separate long-term extension study ( $\geq 2$  years) and be treated with open-label BMS-986165 6 mg QD.

#### **Treatment Arms and Duration:**

**Study treatment:** Subjects in all treatment groups will take oral doses of the investigational product (IP) for 52 weeks during treatment as follows: BMS-986165 6 mg QD, apremilast 30 mg BID (titrated as per label), or placebo QD.

Study Treatment for IM011046		
Medication	Potency	IP/Non-IP
BMS-986165 tablet	6 mg	IP
apremilast tablet	10 mg*	IP
apremilast tablet	20 mg†	IP
apremilast tablet	30 mg‡	IP
placebo tablet	n/a	IP

IP = investigational product; n/a = not applicable

\*Used for titration Day 1 through Day 3 morning dose

†Used for titration Day 3 evening dose through Day 5 morning dose.

‡From Day 5 evening dose onwards

#### **Statistical Methods**

##### General Methodology

The primary efficacy analysis population will be the Full Analysis Set (FAS). The FAS will include all randomized subjects who are dispensed study drug.

The analysis model for the coprimary efficacy endpoints and secondary binary endpoints will use stratified Cochran-Mantel-Haenszel (CMH) tests stratified by the factors used for randomization (see Sec. 4.1.2) to compare the response rates of BMS-986165 6 mg QD to placebo or apremilast as applicable. If expected cell counts are not sufficient for each strata level, then strata levels will be combined for the analysis. Nonresponder imputation will be used for binary endpoints for subjects who discontinue study or treatment of study prior to Week 16, start a protocol prohibited medication/therapy that could improve psoriasis during the first 16 weeks of treatment, or who have otherwise missing endpoint data at the specified timepoint.

The analysis model for continuous secondary endpoints will use analysis of covariance (ANCOVA) with treatment and the factors used for randomization as fixed effects. The baseline value will be added into the model as a covariate. Treatment differences based on least-squares (LS) means and the corresponding 2-sided 95% confidence intervals (CIs) will be provided for the difference between BMS-986165 6 mg QD and placebo or apremilast depending on the endpoint being assessed.

#### Testing Strategy for Efficacy Endpoints

The primary family of coprimary endpoints will each be tested at a Type I error=0.05 first, and if significant for both endpoints, testing will proceed for the secondary family of key secondary endpoints [REDACTED]. The primary family of coprimary endpoints will be the serial gatekeeper for proceeding with testing of the secondary family of key secondary efficacy endpoints.

Primary Family – Coprimary endpoints compared with placebo; both must be significant at a Type I error=0.05 in order to proceed with the secondary family tests for the key secondary endpoints:

[figure not shown]
- Primary 1: Proportion of subjects who achieve sPGA 0/1 at Week 16
- Primary 2: Proportion of subjects who achieve PASI 75 at Week 16

In order to control for Type I error rate inflation within the secondary family of key secondary endpoints, separate testing branches with a 2-sided Type I error=0.025 will be used for comparisons of BMS-986165 6 mg QD compared to placebo and BMS-986165 6 mg QD compared to apremilast. A hierarchical testing method within each testing branch will be implemented for the key secondary endpoints. The hierarchical test may only proceed to the next key secondary endpoint within each testing branch if the null hypothesis is rejected a Type I error=0.025. If an endpoint fails at any step, then all subsequent p-values will be considered descriptive.

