### **4.2 Number of Subjects**

Approximately 600 qualified subjects will be randomized in a 2:1:1 ratio to BMS-986165 6 mg QD, apremilast 30 mg BID, and placebo, respectively. [REDACTED]

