## 2.5 Changes in Statistical Considerations from the Protocol

The following is a list of the important changes in the SAP from the Statistical Considerations section in the protocol:

- The hierarchical testing order for the key secondary endpoints has been updated and two separate hierarchies have been provided, one for US submission and one for ex-US submission (see [Tables 1](#) and [2](#) in Sec. 6.1.3). The update to the hierarchies are due to emerging information from clinical trials conducted with other agents recently approved for the treatment of psoriasis. The hierarchies presented in this document supersede the one that is in the protocol.

Sponsor: Bristol-Myers Squibb

Protocol no: IM011046

- Key secondary endpoints were added for the comparison of BMS-986165 to apremilast for sPGA 0/1, PASI 75, and PASI 90 at Week 24.
- Imputation methods were updated to remove the prohibited medication/therapy criteria for binary and continuous endpoints.
- The Full Analysis Set was changed from “all subjects who were randomized to receive assigned study treatment” in the protocol to “all subjects who are randomized”.
- The list of relevant protocol deviations provided in the protocol was updated for determination of the Per Protocol population.
- Logistic regression analyses for binary endpoints were removed as these are similar to the CMH analyses.

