### 6.1 Efficacy Analyses

All efficacy analyses will be performed using the FAS, unless otherwise specified.

Tests of significance of BMS-986165 6 mg QD vs. placebo for the coprimary endpoints will be two-sided with a significance level of 0.05. Both coprimary endpoints need to demonstrate statistical significance to result in a successful study.

The key secondary endpoints will be tested with a two-sided significance level of 0.025 to compare BMS-986165 6mg QD vs. placebo and vs. apremilast. A hierarchical testing approach will be used for testing of

Sponsor: Bristol-Myers Squibb

Protocol no: IM011046

key secondary endpoints (see [Section 6.1.3](#)). Two-sided 95% confidence intervals (CIs) will be provided for all efficacy estimates. [REDACTED]

Coprimary and key secondary efficacy endpoints will be displayed graphically by treatment group and visit, as applicable. All efficacy endpoints will be summarized descriptively.

Due to small sample sizes in China and Japan and differences in stratification factors, analyses will be stratified by a combination of the stratification factors used in randomization. The stratified levels are provided below:

- US/PRIOR USE/< 90 KG
- US/PRIOR USE/≥90 KG
- US/NAÏVE/<90 KG
- US/NAÏVE/≥90 KG
- ROW/PRIOR USE/< 90 KG
- ROW/PRIOR USE/≥90 KG
- ROW/NAÏVE/<90 KG
- ROW/NAÏVE/≥90 KG
- JAPAN/PRIOR USE
- JAPAN/NAÏVE
- CHINA/PRIOR USE
- CHINA/NAÏVE

If there is not at least one subject per treatment group in each of the China and Japan strata, then these regions will be collapsed together to form the following stratified levels for analyses:

- US/PRIOR USE/< 90 KG
- US/PRIOR USE/≥90 KG
- US/NAÏVE/<90 KG
- US/NAÏVE/≥90 KG
- ROW/PRIOR USE/< 90 KG
- ROW/PRIOR USE/≥90 KG
- ROW/NAÏVE/<90 KG
- ROW/NAÏVE/≥90 KG
- ASIA/PRIOR USE
- ASIA/NAÏVE

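### As far as the public text shows, neither key secondary branch passes on its 0.025 once it is fully rejected: a valid and conservative rule that leaves some power unused

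*Protocol*

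**What the plan says.** The coprimaries act as a gate: "both must be significant at a Type I error=0.05 in order to proceed with the secondary family tests for the key secondary endpoints" (protocol synopsis, Testing Strategy for Efficacy Endpoints). SAP 6.1 agrees that tests "for the coprimary endpoints will be two-sided with a significance level of 0.05".

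Behind the gate the synopsis sets up two branches, one per comparator: "separate testing branches with a 2-sided Type I error=0.025 will be used for comparisons of BMS-986165 6 mg QD compared to placebo", and likewise for apremilast. Each branch is a fixed sequence. Testing "may only proceed to the next key secondary endpoint within each testing branch if the null hypothesis is rejected a Type I error=0.025". The consequence of a failure is also stated: "If an endpoint fails at any step, then all subsequent p-values will be considered descriptive".

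SAP 6.1 gives the same level for both comparators: "The key secondary endpoints will be tested with a two-sided significance level of 0.025". It then refers to SAP 6.1.3 for the hierarchical method. SAP 2.5 places the US and ex-US hierarchies in Tables 1 and 2 of that section and adds: "The hierarchies presented in this document supersede the one that is in the protocol". Section 6.1.3 is not in the public text.

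**The concern.** The two levels add up to the 0.05 that the gate releases. If every hypothesis in one branch has been rejected, that branch has no further use for its 0.025, and a standard graphical procedure would let the other branch go on at 0.05. The visible rule holds the other branch at 0.025 regardless.

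This matters mainly for the apremilast branch, which carries the active-comparator objectives. SAP 4.1.2.2 lists 13 key secondary endpoints there: seven at Week 16, three at Week 24, and three requiring response at both Week 24 and Week 52. In a fixed sequence, one p-value between 0.025 and 0.05 makes every later endpoint descriptive, so a small loss at one step carries through the rest of the branch.

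**Working it through.** **Inputs from the documents.** Alpha is 0.025 per branch, two-sided (synopsis; SAP 6.1). Sample size: "Approximately 600 qualified subjects will be randomized in a 2:1:1 ratio to BMS-986165 6 mg QD, apremilast 30 mg BID, and placebo" (protocol 4.2), so about 300, 150 and 150. SAP 4.1.2.1 lists seven placebo endpoints, one of them (DLQI 0/1) for ex-US only, so six for the US. The apremilast branch has 13. Phase 2 PASI 75 rates were 6.7% on placebo and 68.9% on 3 mg BID (protocol 2.1).

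**Inputs assumed.** The documents give no apremilast response rates, and no power calculation is visible. Comparator rates, differences and correlations below are assumptions.

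1. **The plan's own figure.** 0.025 + 0.025 = 0.05. The split is exact.

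2. **Error control with transfer.** There are two cases.
   - Both branches contain a true null. Neither branch can be completed before a false rejection occurs, so the first true null in each is tested at 0.025. The total is at most 0.025 + 0.025 = 0.05.
   - Only one branch contains true nulls. The first of them is tested at 0.05 at most, so the error is at most 0.05. Without transfer it is at most 0.025.

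3. **Simulation.** 200,000 replicates, 6 placebo and 13 apremilast endpoints, within-arm correlation 0.6, shared BMS-986165 arm. The Monte Carlo standard error near 0.05 is √(0.05 × 0.95 / 200,000) ≈ 0.0005.

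| Configuration | Error, fixed branches | Error, with transfer |
|---|---|---|
| All nulls true | 0.0493 | 0.0493 |
| Placebo branch all false, apremilast branch all null | 0.0250 | 0.0501 |
| Apremilast branch all false, placebo branch all null | 0.0253 | 0.0503 |

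4. **One test.** Power of 80% at 0.025 implies a non-centrality of 2.241 + 0.842 = 3.083. At 0.05, power is Φ(3.083 − 1.960) = Φ(1.123) = 86.9%. In the same way 50% becomes 61.1%, 70% becomes 79.0%, and 90% becomes 94.1%.

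5. **In proportions, 300 vs 150.** Power = Φ[(Δ − z·SE₀)/SE₁], with SE₀ pooled and SE₁ unpooled. For an assumed 45% vs 30%: the pooled rate is (300 × 0.45 + 150 × 0.30)/450 = 0.40. SE₀ = √(0.24 × (1/300 + 1/150)) = 0.0490, and SE₁ = √(0.2475/300 + 0.21/150) = 0.0472. This gives Φ(0.852) = 80.3% at 0.025 and Φ(1.144) = 87.4% at 0.05. For 50% vs 30% the figures are 97.0% and 98.5%. Over comparator rates of 10% to 40% and differences of 8 to 20 points, the gain per test runs from 0.1 to about 12 points.

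6. **The whole apremilast branch.** Same simulation, about 80% power per apremilast test at 0.025, five placebo endpoints practically certain, and the power of the last placebo endpoint varied.

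| Power of last placebo endpoint | All 13 rejected, fixed | All 13 rejected, with transfer |
|---|---|---|
| About 100% | 40.0% | 53.2% |
| 77.6% | 40.2% | 50.6% |
| 40.5% | 40.2% | 45.6% |
| 10.8% | 40.2% | 41.5% |

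7. **Where the split costs nothing.** At the Phase 2 PASI 75 rates, power against placebo at 0.025 is already about 100%.

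**The case against.** **The governing section cannot be read.** SAP 6.1.3 supersedes the protocol's hierarchy, and the explicit stopping rule stands only in the synopsis. A reader might infer that the plan definitely has no transfer. The documents do not support that: a rule in a withheld section is not a missing rule. What they do support is narrower. Both visible statements give a flat 0.025, and the synopsis ties each step to rejection at that level.

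**Fixed branches give stricter protection in some cases.** A reader might also infer that the unused alpha buys nothing. That is true only against the 0.05 target. With one branch all false and the other all null, the error is 0.025 without transfer and 0.050 with it. A sponsor may choose the stricter rule.

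**The gain is conditional.** It arises only if one branch is rejected to its last endpoint while a test in the other has a p-value between 0.025 and 0.05. The placebo branch includes PGA-F 0/1 in subjects with a baseline score of at least 3, a subset of unstated size, and ex-US it also includes DLQI 0/1. If that branch is seldom completed, little is gained. If the apremilast effects are large, little is needed. This stands, and it limits the size of the point.

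**It is a preference.** In part. The present rule is valid. But transfer rejects everything the present rule rejects and sometimes more, within the plan's own 0.05 and with no extra data.

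**Conclusion.** The point holds as an optional efficiency gain. On the visible text, each key secondary branch stays at two-sided 0.025 even after the other is fully rejected, so up to half of the 0.05 can go unused. It would be wrong to read this as a flaw in error control, a bias, or an invalid test.

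The size is conditional: about 7 points for a single test with 80% power at 0.025, if the other branch is completed. For the full apremilast branch, about 40% becomes 42% to 53%. That range assumes 80% power per test, correlation 0.6, and the other five placebo endpoints practically certain. Further weak placebo endpoints would pull it back towards 40%. Because no apremilast rates are given, a loss of power for this trial is possible but not demonstrated.

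**What to change.** First check SAP 6.1.3. If it has no transfer, add one sentence there and in SAP 6.1, separately for the US and the ex-US hierarchy: if every hypothesis in one branch is rejected at 0.025, its alpha passes to the other branch, which is then tested in its fixed order at 0.05. Write it in both directions, since a completed apremilast branch could equally help a weak placebo endpoint such as PGA-F. If 6.1.3 already passes alpha on, amend the flat 0.025 in SAP 6.1 and the synopsis to match.

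The cost is SAP wording, with no added subjects, visits or data. The change must be made before the randomization codes are opened, which SAP 7.2 places after database lock. The sponsor gives up only the extra strictness below 0.05 shown in the working; if it prefers to keep that, the plan can stand as it is.
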